3.7.1 Prohibited Medications

Use of the following products during the study is prohibited: any known 5-HT2A receptor antagonist or inverse agonist, any moderate or strong CYP3A4 inhibitor or any CYP3A4 inducer, or any drugs with known psychotropic properties other than those listed in [Section 6.7](#) or any non-psychotropic drugs with potential central nervous system effects.

3.8 Treatment After Discontinuation of Study Drug or from the Study

Patients whose MDD symptoms worsen or are determined by the Investigator not to be adequately controlled prior to completing the DBTP may be discontinued from the DBTP in order to start appropriate treatment at the Investigator's discretion. The Investigator will refer the study subject to their provider for new treatment and will not be provide the treatment themselves. Patients who initiate a new treatment during the study must be discontinued from the study drug.

Patients who discontinue study drug prior to Week 6 but agree to continue participation in the Double-blind Treatment Period (DBTP) should be seen at all subsequent protocol-defined visits up to week 6 and should also return for the SFU Visit. Study drug will no longer be dispensed for these patients and the clinical management of these patients will be at the discretion of the Investigator;

Patients who discontinue study drug prior to Week 6 and do not agree to continue participation in the DBTP should be seen for an early termination (ET) Visit as soon as possible and should also return for the SFU Visit 1 week after the ET Visit. Study drug will no longer be dispensed for these patients.

3.9 Contraceptive Precautions

WOCBP (women of childbearing potential; not surgically sterilized and between menarche and 1-year post-menopause) must agree to use at least 1 highly effective method of contraception from Screening through at Safety follow up one week after the last study drug administration. Women who are not of childbearing potential must be congenitally or surgically sterile (hysterectomy and/or bilateral oophorectomy/salpingo-oophorectomy, as determined by the subject's medical history) or must be post-menopausal. For men with female sexual partners of childbearing potential, examples of medically acceptable forms of contraception include vasectomy or male condom for subjects, plus an additional method of contraception for their female partners

Effective methods of contraception are those that have a failure rate of <1% (when implemented consistently and correctly) and include:

- Intrauterine device (IUD)
- Bilateral tubal ligation, bilateral salpingectomy, or bilateral tubal occlusive procedure
- Hormonal contraceptives (e.g., oral, patch, or injectable)

- A double-barrier protection method (e.g., condom, sponge, or vaginal diaphragm with spermicide cream, foam, or gel)
- Abstinence from heterosexual intercourse is accepted if this is the subject's usual lifestyle and must be continued until at least 2 months after the last dose of study drug.

Women who are lactating are prohibited from participating in the study.

4. Study Procedures

Table 1. outlines the timing of procedures and assessments to be performed throughout the study.

Table 1.

Study Phase	Screening Period	Double-blind Treatment Period							Safety Follow-up Period
Visit Number	1 (Screening)	2 (Baseline)	3	4	5	6	7	8/ET ²	
Study Week	Week -2	Week 1	Week 2	Week 3	Week 4	Week 5	Week 6	Week 7	
Study Day	Up to 15 days prior to baseline	(± 2 days)							
Informed consent	X								
I/E criteria	X	X							
Medical history and demographics	X								
Physical examination	X						X		
Vital signs	X	X	X	X	X	X	X	X	
12-lead ECG	X			X			X		
Clinical laboratory tests									
Hematology	X			X			X	X	
Biochemistry	X							X	
Urinalysis (Dipstick)	X	X							
TSH	X		X					X	
Hepatitis serology	X								
Urine Drug Screen and Breath Alcohol Test	X	X							
Serum/Urine Pregnancy test	X	X							
Study Assessments									
SCID-	X								

Borderline personality disorder module								
Diamond	X							
CAPS-5	X							X
CGI-S	X	X		X		X		X
MCI	X							
MADRS	X	X	X	X	X	X	X	X
C-SSRS	X	X	X	X	X	X	X	X
MGH-ATRQ	X							
GASS			X		X		X	X
GAD-7 QIDS-SR-16, EQ 5D-5L	X	X	X	X	X	X	X	X
PCL-5		X			X		X	X
Trauma Questionnaire	X							
CTQ	X							
EMA	X	X	X	X	X	X	X	X
Study drug dispensing		X	X	X	X	X		
Study drug compliance			X	X	X	X		
fMRI		X						X
Prior/concomitant medication								X
Adverse events								

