7. Females of childbearing potential agree to use at least an acceptable method of birth control (including but not limited to hormonal contraception, intrauterine device, vasectomized partner, bilateral tubal occlusion, condom with or without spermicide, cap with spermicide, diaphragm with spermicide, sponge with spermicide, or double barrier methods) from the time informed consent is provided through the end of the SFU period. *NOTE:* Females of non-childbearing potential (defined as either permanently sterilized, or post-menopausal females [defined as at least one year with no menses without an alternative medical explanation]) are exempt from the birth control requirement.
8. Ability to follow study instructions and likely to complete all required visits.

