Regarding the focus on physical or sexual assault, there are two main reasons. First, the definition of physical and sexual assault can more easily be operationalized through a behavioral description of an event (e.g., has anyone hit you with a fist, has anyone hit you with an object, etc), enabling more precise assessment and detection. Second, there is a robustly elevated risk for mood disorders following assaultive traumas relative to non-assaultive traumas. As such, there is greater clinical need to establish adjunctive treatments among those experiencing assaultive traumas.

14. Participants must have been treated with the same dose of antidepressant therapy for at least 6 weeks, with less than 50% improvement, and be committed to the same stable dosing regimen for the Screening period and for the entire study, at or above the minimally adequate dose in the ATRQ. Documentation of stable and ongoing ADT must be verified by documentation from the subject's psychiatrist, pharmacist, primary care physician or other qualified healthcare professional.

15. Female of childbearing potential and agrees to use at least an acceptable method of birth control (including but not limited to hormonal contraception, intrauterine device, vasectomized partner, bilateral tubal occlusion, condom with or without spermicide, cap with spermicide, diaphragm with spermicide, sponge with spermicide, or double barrier methods) from the time informed consent is provided through the end of the SFU period. **NOTE:** Females of non-childbearing potential (defined as either permanently sterilized, or post-menopausal females [defined as at least one year with no menses without an alternative medical explanation]) are exempt from the birth control requirement.

16. Ability to follow study instructions and likely to complete all required visits.

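### Inclusion criterion 7 accepts a condom without spermicide as sole contraception, while section 3.9 requires a highly effective method from the same women over the same period

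*Protocol*

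**What the plan says.** Three places in the protocol set the rule for women of childbearing potential.

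- **Section 2.1, inclusion criterion 7.** The standard is at least one *acceptable* method. After the hormonal, intrauterine, vasectomized-partner and tubal options, the list continues "condom with or without spermicide, cap with spermicide, diaphragm with spermicide, sponge with spermicide, or double barrier methods". The rule runs "from the time informed consent is provided through the end of the SFU period". The list is open-ended.
- **Item 20, Inclusion/Exclusion Criteria, number 15.** This copy keeps the same standard and the same list: "Female of childbearing potential and agrees to use at least an acceptable method of birth control".
- **Section 3.9, Contraceptive Precautions.** These women "must agree to use at least 1 highly effective method of contraception from Screening through at Safety follow up", which falls one week after the last dose. The only definition that follows is "Effective methods of contraception are those that have a failure rate of <1% (when implemented consistently and correctly". The only barrier entry in the list below it is "A double-barrier protection method (e.g., condom, sponge, or vaginal diaphragm with spermicide cream, foam, or gel".

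Criterion 7 does not refer to section 3.9, and section 3.9 does not refer to criterion 7.

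**The concern.** The two texts cover the same women for the same weeks but ask for different things. Sections 4.2.1 and 4.2.2 move a participant to Baseline and then to randomization on the inclusion and exclusion criteria, and Table 1 schedules that check at Visits 1 and 2. Staff working from that list could properly enrol a woman whose agreed method does not match section 3.9.

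What is at stake is participant safety and a clear rule. The risk text in item 39 says the drug's effects on unborn babies are not fully known. Scheduled pregnancy tests fall only at Screening and Baseline, so during the six weeks of dosing the contraception rule is the main planned safeguard. It should have one meaning.

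**Working it through.** No figure in the protocol needs reproducing. The check sets the two rules side by side.

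| Element | Inclusion criterion 7 (section 2.1; item 20, number 15) | Section 3.9 |
|---|---|---|
| Population | Women of childbearing potential | The same |
| Start | Informed consent | Screening, which begins once consent is signed (section 4.2.1) |
| End | End of safety follow-up | Safety follow-up, one week after the last dose |
| Standard | At least one acceptable method | At least one highly effective method |
| Definition | None beyond the list | Failure rate below 1% with consistent, correct use |
| Barrier methods | Condom with or without spermicide; cap, diaphragm or sponge with spermicide; double barrier as a separate entry | Double-barrier only |

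**Step 1: population and period.** These match. Both rules span 2 weeks of screening + 6 weeks of treatment + 1 week of follow-up = 9 weeks. The difference in standard therefore cannot be explained by a different group or time window.

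**Step 2: terms.** Section 3.9 requires a *highly effective* method, then defines and lists *effective* ones. No other definition is offered, so that list is the only available content for the requirement. The mixed terms are a drafting fault of their own.

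**Step 3: the lone condom.** Criterion 7 lists the condom, with or without spermicide, apart from double-barrier methods, so one condom and nothing else satisfies it. Section 3.9's only barrier entry is double-barrier. A condom with spermicide can be read into that entry. A condom without spermicide is a single barrier and cannot.

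**Step 4: which text governs enrolment.** Sections 4.2.1 and 4.2.2 and Table 1 point to the inclusion and exclusion criteria. Section 3.9 is not named at either step.

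**Result.** A woman who agrees only to a condom without spermicide meets criterion 7 but does not use a method that section 3.9 recognises.

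**The case against.** The strongest reply is that the rules are cumulative. Criterion 7 sets a floor and section 3.9 a stricter duty. A woman who meets the second also meets the first, so staff can comply with both. That is correct as logic, and it means neither rule forces a breach of the other. It does not settle the matter, because the protocol nowhere says the stricter rule prevails and the list that controls randomization does not point to it.

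A second reply is that existing safeguards narrow the harm. This stands. There is a serum test at Screening, and a negative urine test is needed before dosing (exclusion 11; section 8). Further tests may be done at any time at the investigator's discretion (section 8). Pregnancy is a listed reason for discontinuation (section 2.4), and study drug stops (item 39). Item 39 also asks for an effective form of birth control and has the study doctor discuss methods, though it names none.

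Four stronger readings are tempting, and the documents do not support them.

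- *A lone condom is shown to exceed the 1% failure limit.* The protocol gives no failure rate for condoms, and section 3.9's list is not closed. What can be shown is that the method is not listed and that barriers appear only when doubled.
- *The rule for men confirms it.* For male participants the text suggests "vasectomy or male condom for subjects, plus an additional method of contraception for their female partners". It pairs vasectomy with an additional method too, and offers these only as examples, so it says nothing specific about condoms.
- *The share of non-conforming methods measures the problem.* Both lists are open, so there is no meaningful denominator.
- *The abstinence clause should be shortened to match.* For women relying on abstinence it "must be continued until at least 2 months after the last dose of study drug", longer than the general rule. Cutting it would weaken a precaution, and nothing here justifies that.

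**Conclusion.** The inconsistency is real and can be established from the protocol's text alone. The eligibility list accepts a condom without spermicide as sole contraception, and section 3.9 does not recognise that method for the same women over the same roughly 9 weeks.

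The point is minor. The number of women who would rely on that method is not stated and may be 0 of the 50 participants. Pregnancy testing before dosing, discretionary tests later and stopping the drug on pregnancy limit the safety consequence. No endpoint, estimand, power or error-rate consideration is affected.

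The conclusion rests on two readings: that the definition and list in section 3.9 give content to its highly effective requirement, and that staff check eligibility against the criteria as written. A reader might infer that the trial is bound to enrol women in breach of its own rule. The documents do not show that, since staff who also apply section 3.9 would prevent it.

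**What to change.** Make these changes in one edit.

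1. In both copies of criterion 7 (section 2.1; item 20, number 15), replace the acceptable-method standard and its list with the section 3.9 standard and list, or with a cross-reference to section 3.9.
2. Remove the condom without spermicide as a sole method.
3. Use one term, *highly effective*, throughout section 3.9.
4. Match the consent wording to the result.
5. Leave the abstinence duration unchanged.

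Relaxing section 3.9 to the acceptable standard would also restore consistency. Tightening criterion 7 is the more protective choice, given the stated uncertainty about effects on unborn babies.

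The cost is wording only, with no added visit, test or analysis. The downside is that a few women, possibly none of the 50, would have to add or change a method in order to enrol.

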4.1 Informed Consent

Before performing any study-related procedures, the Investigator (or designee) will obtain signed informed consent from the subject.

In the event that rescreening occurs, the individual is required to sign a new ICF and must be assigned a new identification number.

4.2 Order of Assessments

4.2.1 Screening (Visit-1 Week-2)

All subjects agreeing to participate in the study must give informed consent by signing the ICF before any study-related procedures are performed. Screening begins after ICF has been signed and dated by the subject and the Investigator or other appropriate site staff. The duration of the Screening will be 2 weeks.

The following procedures should be performed in order after the ICF is reviewed and signed:

1. Collection of medical and psychiatric history, concomitant medications and demographic information. Physical examination, ECG and pulse oximetry need to be performed, and height, weight, BMI and vital signs recorded.
2. Standardized assessments to include:
Clinician Rater: CAPS-5, MADRS, DIAMOND, SCID borderline personality module, CGI-S, MGH-ATRQ, CSSRS
PROs: GAD-7, QIDS-SR-16, EQ 5D-5L, CTQ, PCL-5, NSW, MCI
3. Collection of urine sample for urinalysis and drug screen analysis.

4. Blood sample collection to obtain hematology, biochemistry, hepatitis B and C, HIV, TSH and FSH data. A serum pregnancy test (b-HCG) is performed at screening for females of childbearing potential.
5. Breath alcohol test.
6. EMA wellness app activation

Subjects that meet all eligibility and inclusion and no exclusion criteria, will undergo Visit 2 (Baseline).

4.2.2 Baseline (Visit 2 Week-1)

Subjects continuing to meet all eligibility and inclusion criteria and no exclusion criteria, will be randomized within each group at Baseline to start the study treatment.

1. Assessment scales: MADRS, CGI-S C-SSRS, HAMD-17, GAD-7, PHQ-9, QIDS-SR-16, and EQ 5D-5L.
2. Vital signs, including body temperature, systolic and diastolic BP, HR, pulse oximetry, and RR measures after the subject has been resting for at least 3 minutes.
3. ECGs taken pre-dose.
4. fMRI will be obtained.
5. EMA wellness App
6. AE if applicable
7. Laboratory tests, consisting of: blood sample for Hematology
8. POC: Urine drug test, pregnancy test (if applicable) and Breath Alcohol test

4.2.3 Double-blind Treatment Visits (Visits 3-7 ;Weeks 2-6)

1. Record AEs as reported by patient or observed by Investigator
2. Review concomitant medications
3. Study drug compliance check, return unused Meds at each visit
4. Vital signs (BP, pulse rate, body temperature, respiratory rate) and weight
5. Assessment Scales: MADRS, CGI-S C-SSRS, HAMD-17, GAD-7, PHQ-9, QIDS-SR-16, EQ 5D-5L and GASS
6. Lab tests for Hematology for CBC will be completed at wee4 and week6 visits and Complete BW similar to screening visit will be completed at Week-7
7. EMA Wellness App (Optional)

7.2.4 Safety Follow up (Visit 8: Week 7)

1. Record AEs as reported by patient or observed by Investigator
2. Review concomitant medications
3. Study drug compliance check, return unused Meds
4. Vital signs (BP, pulse rate, body temperature, respiratory rate) and weight
5. fMRI Assessments.

7.3 Entry Criteria Measurements

7.3.1 Clinician-Administered PTSD Scale for DSM-5 (CAPS-5)

The CAPS-5 is a 30-item, clinician-administered assessment tool used to diagnose and measure the severity of post-traumatic stress disorder (PTSD) according to the DSM-5 criteria. Administered by a trained study staff.¹⁷

7.3.2 Diagnostic Interview for Anxiety, Mood, and other Disorders (DIAMOND)

The Diamond is a semi-structured interview guide to ensure consistency with the DSM 5 diagnostic classification. It is administered by a clinician or trained mental health professional who is familiar with the DSM-5 classification and diagnostic criteria. It provides diagnostic information, including severity, of many DSM-5 disorders, including MDD.¹⁸

7.3.3 Antidepressant Treatment Response Questionnaire (ATRQ)

The ATRQ examines the efficacy and adequacy of any antidepressant treatment in a step-by-step procedure. This widely accepted questionnaire evaluates improvement (0% to 100%) and adequacy (adequate duration and dose)

¹⁹

7.3.4. SCID-5 Borderline Personality Disorder Module.

The SCID-5 borderline personality disorder module is a semi-structured interview for BPD to ensure consistency with DSM-5 criteria. It is administered by a clinician or trained mental health professional who is familiar with the DSM-5 classification and diagnostic criteria.²⁰

7.4 Efficacy Assessments

The Schedule of Assessments ([Table 1](#)) outlines the efficacy assessments to be performed throughout the study and their timing. For assessment scales performed at each visit, MADRS must be the first assessment performed by the rater at the site. Subsequent assessments, following MADRS, can be conducted in any order as determined by the investigator's discretion. The following order of assessments is recommended, from the least to the most invasive procedure: all assessment scales, vital signs, ECGs and lastly blood draw as indicated in [Table 1](#).

7.4.1 Primary Efficacy Assessment -Montgomery-Åsberg Depression Rating Scale (MADRS)

The MADRS is a 10-item questionnaire with each item scored between 0 and 6, resulting in a total score between 0 and 60, with scores above 34 indicating severe depression. Higher MADRS scores indicate more severe depression. The questionnaire is most frequently used in clinical studies to measure outcomes in antidepressant efficacy studies. This scale exhibits construct validity (internal homogeneity) and the concepts of endogenous and non-endogenous depression. The questionnaire includes questions on the following symptoms: (1) apparent sadness; (2) reported sadness; (3) inner tension; (4) reduced sleep; (5) reduced appetite; (6) concentration difficulties; (7) lassitude; (8) inability to feel; (9) pessimistic thoughts; (10) suicidal thoughts. The MADRS must be administered using the Structured Interview Guide for the MADRS (SIGMA). The MADRS total score at screening is a major inclusion criterion of the study, as well as the primary outcome measure for the study. The MADRS will be administered at Screening and Baseline and subsequent weekly visits.²¹

7.4.2 Secondary Efficacy Assessment-Clinical Global Impression of Severity (CGI-S)

The CGI-S measures the severity of the disease using a 7-point Likert scale ranging from 1=normal, not at all ill to 7=among the most extremely ill subjects²²

7.4.3 Ecological Momentary Assessment.

Using EMA Wellness software, participants will complete a daily assessment of mood and anxiety as well as positive and negative affectivity ratings twice daily.

Specific assessments of mood and anxiety include: PHQ-9; GAD-7. Specific assessment of positive and negative affect: happy, sad, anxious, relaxed. Participants start EMA assessment during two-week run-in period. QOL assessment once a week will also occur.

7.5 Columbia–Suicide Severity Rating Scale

The C-SSRS is a clinician-rated instrument that reports the severity of both suicidal ideation and behavior ²³The C-SSRS will be completed by a trained and approved rater. The C-SSRS will be completed at all study visits. At Screening (Visit 1), the C-SSRS will be completed for the patient's lifetime history of suicidal ideation and behavior ("Baseline/Screening" version). At all other visits, the C-SSRS will be completed for suicidal ideation and behavior since the previous visit ("Since Last Visit" version).

7.6 Extrapyramidal Symptom Assessment

Glasgow Antipsychotic symptom scale: The Glasgow Antipsychotic Side-effect Scale is a patient self-report scale used to screen for antipsychotic side effects.²⁴

7.7 Vital Signs

Vital signs (systolic and diastolic blood pressure [BP], pulse rate, respiratory rate, and body temperature) will be assessed at every visit during the study as specified in the Schedule of Assessments ([Table 1](#).)

Blood pressure and pulse rate will be measured in both the supine and standing positions with measurements performed after at least 5 minutes lying down and then at least 3 minutes after rising from the supine position to the standing position. BP may be measured using the same method consistently for each patient throughout the study.

Body weight, and height will be assessed as specified in the Schedule of Assessments (Table 1.)

7.8 Electrocardiogram

A 12-lead ECG will be performed as specified in the Schedule of assessments (Table 1.) Each ECG assessment will be conducted after the patient has been resting quietly in the supine position and will comprise ten-second epochs from 12-lead ECGs. ECG parameters to be measured include HR, QRS, PR, QT, QTcB, QTcF and RR intervals.

8. Clinical Laboratory Assessments

Blood and urine samples for clinical laboratory tests will be collected as specified in the Schedule of Evaluations Table 4. If possible, patients should fast for at least 8 hours before the collection of clinical laboratory blood tests. During Screening, the Investigator/sub-investigator will assess the clinical significance of any values that are outside the reference ranges provided by the central laboratory. Patients with abnormal screening laboratory results judged to be clinically significant will be excluded from the study.

Laboratory results will be reviewed by the Investigator/Sub-Investigator throughout the study. The following clinical laboratory levels will be measured:

- Hematology: hematocrit; hemoglobin; HbA1c (at Screening [Visit 1] only); red blood cell count with indices (mean corpuscular volume, mean corpuscular hemoglobin, and mean corpuscular hemoglobin concentration); reticulocytes; white blood cell count and differential (neutrophils, absolute neutrophil count, lymphocytes, monocytes, eosinophils, and basophils) reported as percent (%) and absolute values; and platelet count.
- Chemistry: albumin; ALP; ALT; AST; bilirubin (total, direct); blood urea nitrogen; calcium; chloride; cholesterol (total; high-density lipoprotein [HDL] and low-density lipoprotein [LDL] will be calculated and reported); creatinine; creatine phosphokinase; gamma-glutamyl transferase; glucose; insulin; lactate dehydrogenase; phosphate; potassium; prolactin; sodium; triglycerides; total protein; uric acid. TSH (reflex free T3 and free T4) will be measured at Screening (Visit 1) and Visit 7 (Week-6)/ET only.
 - Urinalysis: macroscopic (pH, specific gravity, glucose, protein, ketones, bilirubin, nitrites, blood) and microscopic (red blood cells/high-power field, white blood cells/high-power field, casts, epithelial cells, crystals, granulation). Urine Drug Screen (UDS): Urine drug tests for amphetamines, barbiturates, benzodiazepines, cannabinoids, cocaine, methadone, or opioids/opiates will be performed Screening (Visit 1) and Visit 6 (Day 22)/ET.
 - Alcohol Testing: An alcohol test (urine or breath) will be performed at Screening (Visit 1) and Visit 7 (Week-6)/ET.
 - Urine and serum pregnancy tests: Female patients who are of childbearing potential will undergo a serum pregnancy test at Screening (Visit 1), and a urine pregnancy test at Baseline (Visit 2/Week 1). Unscheduled serum/urine pregnancy tests may be administered at any time at the discretion of the Investigator. Serum pregnancy testing will be performed using blood collected as part of protocol-specified sample; urine pregnancy testing will use a urine dipstick.
 - Hepatitis screening: Blood samples will be collected at Screening (Visit 1) from all patients in order to perform serology testing for hepatitis B and hepatitis C.

Table 4.

Hematology	Serum Chemistry	Urinalysis (Dipstick)* (onsite)
------------	-----------------	---------------------------------

hemoglobin	eGFR (screening only)	pH
hematocrit	HbA1c (Screening only)	specific gravity
erythrocytes	creatinine	protein
platelets	total bilirubin (and fractionation of bilirubin >ULN)	glucose
leukocytes with differential (including eosinophils, neutrophils, basophils, lymphocytes and monocytes)	albumin	ketones
	blood urea nitrogen	bilirubin
	total protein	occult blood
	alkaline phosphatase	nitrite
	aspartate aminotransferase	urobilinogen
	alanine aminotransferase	leukocyte esterase
	glucose	
	sodium	
	potassium	
	magnesium	
	calcium	
	chloride	
	phosphate	
	bicarbonate	
	TSH (Screening only)	

* Reflex microscopy when indicated

Pregnancy testing: A serum FSH test will be conducted for all females at Screening. A urine pregnancy test, and serum pregnancy test (b-HCG) will be conducted on all WOCBP at Screening. Negative pregnancy test results are required for enrollment in the study; a negative urine pregnancy test will be required at Baseline (Week 1) for confirmation.

Urine drug and alcohol screen at Screening and Baseline: Drug and alcohol abuse testing will be performed according to the assessment schedule. Screening for drugs will include: tetrahydrocannabinol, opiates (including oxycodone), amphetamines, cocaine, and benzodiazepines.

Serologic testing for hepatitis B surface antigens, hepatitis C antibodies, and HIV antibody testing will be performed at the Screening visit.

9. Adverse Events

The Investigator and research study staff will responsible for the detection, documentation, classification, reporting, and follow-up of events meeting the definition of an AE or SAE. Procedures for managing AEs and SAEs are detailed in the research site's SOPs.

